### 1. SYNOPSIS

**Protocol Number: STX-101-02** 

#### Name of Sponsor/Company:

Spirita Oncology, LLC

### Name of Investigational Product:

E6201

Name of Active Ingredient: (3*S*,4*R*,5*Z*,8*S*,9*S*,11*E*)-14-

(Ethylamino)-8,9,16-trihydroxy-3,4-dimethyl-3,4,9,10-tetrahydro-1*H*-2-benzoxacyclotetradecine-1,7(8*H*)-dione

**Title of Study:** A Phase 1 Study of E6201 for the Treatment of Central Nervous System (CNS) Metastases From *BRAF* V600-Mutated Metastatic Melanoma

**Principal Investigator(s):** [name] (University of Arizona) (Study Chair), and additional study centers as needed to ensure timely study accrual.

Study Period (30 months):	Phase of Development: 1
Date First Subject Enrolled: November 16, 2018	
Estimated Date Last Subject Completed: April 2021	

### **Objectives:**

#### Primary:

• To determine the overall rate of response of brain metastases in subjects with CNS metastases due to metastatic melanoma with a *BRAF* V600 mutation who have relapsed or progressed from initial or systemic disease

### Secondary:

- To determine the intracranial disease duration of response, duration of stable disease (SD) and time to progression of CNS metastases
- To determine the objective response rate of systemic disease other than in the CNS
- To evaluate progression-free survival (PFS)
- To evaluate overall survival (OS)
- To evaluate the impact of the *BRAF* mutational status (e.g., type, heterozygosity or homozygosity) in archival tissue with clinical outcome
- To evaluate the safety of E6201as monotherapy and in combination with dabrafenib in this population

#### Methodology:

This is a Phase 1 study of E6201 for the treatment of CNS metastases in BRAF V600-mutated metastatic melanoma. A total of N = 28 - 34 subjects with melanoma metastasized to the CNS will be included. Selected subjects will be: both males and females age  $\geq 18$  years; histologically confirmed melanoma with BRAF V600 mutation with CNS metastasis; archived tumor sample from the primary, recurrent or metastatic disease with documented BRAF mutation; no prior treatment with BRAF or MEK inhibitors for systemic disease; recovered from all acute toxicities ( $\geq$  Grade 1) due to prior immunotherapy; determined to have adequate renal and hepatic function; and no known history of significant cardiac disease.

Confidential 3
December 31, 2019 Protocol Amendment 4

#### **Protocol Number: STX-101-02**

Monotherapy Safety Run-in Phase: Following screening, a total of 4 subjects were enrolled. E6201 was administered by intravenous (IV) infusion over a 2-hour period at a dose of 320 mg/m² twice weekly (Days 1, 4, 8, 11, 15 and 18) for 3 weeks, repeated every 28 days (1 cycle) until progression of disease, observation of unacceptable adverse events, intercurrent illness or changes in the subject's condition that prevented further study participation.

Combination Safety Run-in Phase: Following screening, a total of 6 - 12 subjects are anticipated to establish the recommended doses of E6201 plus dabrafenib. E6201 will be administered by IV infusion over a 2-hour period twice weekly (Days 1, 4, 8, 11, 15 and 18) repeated every 28 days plus dabrafenib orally twice daily (=1 cycle), according to the schedule below.

Dose Level	E6201 (IV)	Dabrafenib (PO)
1	320 mg/m² (MTD monotherapy)	150 mg BID (market dose)
-1ª	240 mg/m² (Dose Level -1)	150 mg BID
-2ª	240 mg/m² (Dose Level -1)	100 mg BID (Dose Level -1)
-3ª	160 mg/m² (Dose Level -2)	100 mg BID (Dose Level -1)
-4 a	160 mg/m² (Dose Level -2)	75 mg BID (Dose Level -2)
-5ª	160 mg/m² (Dose Level -2)	50 mg BID (Dose Level -3)

<sup>a If necessary based on DLT ( $\geq 1$  of 3 or  $\geq 2$  of 6 subjects experience DLT at the previous dose level)

Subjects who demonstrate clinical benefit (objective response or stable disease) will be allowed to continue therapy with E6201 plus dabrafenib until progression of disease, observation of unacceptable adverse events, intercurrent illness or changes in the subject's condition that prevents further study participation.

Dose-limiting toxicity (DLT) is defined as any one of the following events:

- Grade 4 hematologic toxicity for > 1 day
- Grade 3 hematologic toxicity with complications (e.g., thrombocytopenia with bleeding)
- Failure of Grade 3 thrombocytopenia, absolute neutrophil count (ANC), hemoglobin to recover to Grade ≤ 1 within 4 weeks despite the use of platelet and red blood cell (RBC) transfusions and/or growth factors
- ≥ Grade 3 non-hematologic toxicity not due to disease progression (excluding Grade 3 nausea, vomiting or diarrhea that is adequately controlled with supportive care and resolves to ≤ Grade 2 within 48 hours, or Grade 3 electrolyte disturbances responsive to correction within 24 hours)
- $\geq$  Grade 3 liver function tests (LFTs) lasting > 72 hours
- Treatment interruption > 14 days due to toxicity
- Other important medical event

Subjects who require a dose reduction due to toxicity will be considered to have had a DLT.

No DLTs were experienced in the Monotherapy Safety Run-in Phase. If a DLT is experienced in  $\geq 2$  of 6 subjects in the Combination Safety Run-in Phase during Cycle 1, no further subjects will be enrolled at that dose level. Subjects who experience a DLT may continue treatment at the next lower dose level until disease progression or unacceptable toxicity. The maximum tolerated dose (MTD) is defined as the doses of E6201 plus dabrafenib at which  $\leq 1$  of 6 subjects experiences a DLT.

Confidential 4
December 31, 2019 Protocol Amendment 4

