#### **Protocol Number: STX-101-02**

Subjects who experience E6201- and/or dabrafenib-related toxicity requiring a dose reduction may continue treatment at the next lower dose level for either drug until disease progression or unacceptable toxicity.

E6201 dose reductions for suspected E6201-related toxicity will be 240 mg/m^2 twice weekly (Dose Level -1) and 160 mg/m^2 twice weekly (Dose Level -2), administered over the same schedule as above, Days 1, 4, 8, 11, 15 and 18, repeated every 28 days.

Dabrafenib dose reductions for suspected dabrafenib-related toxicity will be 100 mg (Dose Level -1), 75 mg (Dose Level -2) and 50 mg (Dose Level -3) orally twice daily, according to the U.S. Product Label.

A total of 6 subjects will be treated at the combined MTD doses for both drugs in the Combination Safety Run-in Phase before beginning the Expansion Phase.

Expansion Phase: Following screening, an additional cohort of up to N=18 subjects will be treated at the E6201 plus dabrafenib combined MTD. Subjects treated at the MTD in the Combination Safety Run-in Phase will count towards accrual in the Expansion Phase. E6201 will be administered by IV infusion over a 2-hour period at the MTD and schedule determined in the Combination Safety Run-in phase, repeated every 28 days (=1 cycle), and dabrafenib will be administered orally twice daily at the MTD determined in the Combined Safety Run-in phase. Both regimens will be subject to dose reductions for toxicity, as described. Subjects who demonstrate clinical benefit (objective response or stable disease) will be allowed to continue therapy with E6201 plus dabrafenib until progression of disease, observation of unacceptable adverse events, intercurrent illness or changes in the subject's condition that prevents further study participation.

During the study, a Safety Review Committee (SRC), consisting of the actively recruiting investigators, the Sponsor Medical Monitor and study staff will review data from the Monotherapy and Combination Safety Run-in Phases before beginning the Expansion Phase, and will review data from the Expansion Phase on an ongoing basis.

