#### **Protocol Number: STX-101-02**

disease, observation of unacceptable adverse events, intercurrent illness or changes in the subject's condition that prevents further study participation.

Number of Subjects and Centers (planned): A total of 4 subjects were enrolled in the Monotherapy Safety Run-in Phase. A total of 6 - 12 subjects are anticipated in the Combination Safety Run-in Phase. A total of up to 18 subjects will be enrolled in the Expansion Phase for a total N = 28 - 34 for the study. Study centers include University of Arizona ([name] - Study Chair) and additional study centers as needed to ensure timely study accrual.

**Duration of Study:** Accrual is expected to be 24 months, with the last subject followed for up to 6 months. The total study duration is expected to be 30 months. The anticipated accrual rate is 1-2 subjects per month.

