# **5.2.** Number of Subjects and Centers

A total of 4 subjects were enrolled in the Monotherapy Safety Run-in Phase. A total of 6-12 subjects are anticipated in the Combination Safety Run-in Phase. A total of up to 18 subjects will be enrolled in the Expansion Phase for a total of N=28-34 for the study. Study centers include University of Arizona ([name]), and additional study centers as needed to ensure timely accrual to the study.

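### The stated run-in of 6-12 and study total of N = 28-34 do not agree with the plan's own six-level dose table and its rule for counting run-in subjects

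*Combined protocol and SAP*

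**What the plan says.** The size statements appear in the Synopsis (Methodology; Number of Subjects and Centers) and in Sections 5.1 and 5.2.

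- **Monotherapy Run-in:** "A total of 4 subjects were enrolled in the Monotherapy Safety Run-in Phase".
- **Combination Run-in:** "a total of 6 - 12 subjects are anticipated to establish the recommended doses of E6201 plus dabrafenib". Section 5.2 gives the same range and the same verb: 6-12 "subjects are anticipated in the Combination Safety Run-in Phase".
- **Expansion and total:** "A total of up to 18 subjects will be enrolled in the Expansion Phase for a total N = 28 - 34". The Methodology text is firmer: "A total of N = 28 - 34 subjects with melanoma metastasized to the CNS will be included".

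The rules that determine those sizes are in the Synopsis and Section 5.1.

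- The table lists six combination levels: 1, -1, -2, -3, -4 and -5.
- Footnote a opens a lower level, if necessary, when at least 1 of 3 or at least 2 of 6 "subjects experience DLT at the previous dose level".
- The MTD is the dose pair at which no more than 1 of 6 subjects has a DLT.
- Before the Expansion begins, "A total of 6 subjects will be treated at the combined MTD doses for both drugs".
- Run-in subjects treated at the MTD are credited to the Expansion's enrolment.

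Section 6.3.2 adds replacement of certain subjects who do not complete Cycle 1. Neither size range states an allowance for this.

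**The concern.** A run-in of 12 leaves only six subjects for rejected levels once six are reserved for the MTD. That looks too few for a table that permits five step-downs. The total is a plain sum of the three phases, although the same text says that some subjects belong to two of them.

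The stated sample size is what an ethics board, a site or a later reader relies on. If it does not follow from the design, a run-in of ordinary length could appear to breach the protocol, and a trial that runs exactly as planned could finish below its stated minimum. The plan also does not say what happens if 12 run-in subjects are used without an MTD, or if Level -5 fails. The Expansion supplies most of the 18 subjects for the primary rule of 3 or more responses (Section 11.1), so the reader needs to know how the run-in can end.

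**Working it through.** **1. Reproduce the stated total.** Monotherapy 4, run-in 6 to 12, Expansion 18:

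- 4 + 6 + 18 = 28
- 4 + 12 + 18 = 34

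This matches 28-34 exactly, so the total was formed without the counting rule.

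**2. Apply the counting rule.** Six run-in subjects at the MTD count toward the 18, so 18 - 6 = 12 more are needed. Total = 4 + run-in + 12:

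- run-in of 6: 4 + 6 + 12 = 22
- run-in of 12: 4 + 12 + 12 = 28
- run-in of 18: 4 + 18 + 12 = 34

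A total of 28-34 therefore corresponds to a run-in of 12-18, not 6-12.

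**3. Run-in size implied by the table.** Let k be the number of rejected levels. From footnote a, each uses 3 to 6 subjects. The MTD level then holds 6. The run-in is 3k + 6 to 6k + 6.

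| MTD level | k | Run-in | Study total (4 + run-in + 12) |
|---|---|---|---|
| 1 | 0 | 6 | 22 |
| -1 | 1 | 9-12 | 25-28 |
| -2 | 2 | 12-18 | 28-34 |
| -3 | 3 | 15-24 | 31-40 |
| -4 | 4 | 18-30 | 34-46 |
| -5 | 5 | 21-36 | 37-52 |

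Twelve subjects are enough for Level -2 only if both rejected levels stop at 3. If each rejected level uses 6, 12 subjects reach only Level -1. Level -5 exceeds a total of 34 in every case. Replacements come on top.

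**4. How often this matters.** The documents give no DLT rate for the combination, so the rates below are assumptions. Two readings of the first-three rule are shown:

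- Reading A follows footnote a: leave the level at 1 or more of 3, otherwise treat 6 and leave at 2 or more.
- Reading B leaves at 2 or more of 3, otherwise treats 6 and leaves at 2 or more. It is included because one DLT in the first three is still compatible with the MTD definition of at most 1 of 6.

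Example, flat 20%, reading A. A level:

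- fails at 3 with probability 1 - 0.8³ = 0.488
- fails at 6 with probability 0.512 × 0.104 = 0.053
- passes with probability 0.512 × 0.896 = 0.459

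The paths that finish within 12 are a pass at once, one failure (at 3 or at 6) then a pass, and two failures at 3 then a pass:

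0.459 × (1 + 0.488 + 0.053 + 0.488²) = 0.816, so P(no MTD within 12) = 0.184.

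The same exact enumeration over all six levels gives the table below. By step 2, the total stays within 34 when an MTD is found with a run-in of at most 18.

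| Assumed DLT rate | No MTD within 12 run-in subjects (A / B) | Total above 34, or no MTD at any level (A / B) |
|---|---|---|
| flat 10% | 3.3% / 1.2% | 0.4% / 0.1% |
| flat 20% | 18.4% / 11.2% | 6.2% / 3.5% |
| 30% at Level 1, falling 5 points per level | 29.7% / 24.8% | 6.1% / 7.4% |
| 40% at Level 1, falling 5 points per level | 53.7% / 48.0% | 23.1% / 24.0% |

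**The case against.** The strongest reply is that 6-12 is only anticipated and the lower levels are used only if necessary. An expected range need not cover the worst case, nothing forbids a thirteenth run-in subject, and at a DLT rate near 10% twelve subjects nearly always suffice. All of this stands. It rules out three stronger conclusions that a reader might draw.

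- **That Levels -3 to -5 cannot be reached.** This needs 12 to be a hard limit, and no section says so. Even the total of 34 leaves room for 18 run-in subjects, enough for Level -4 when each rejected level uses 3.
- **That the Expansion could not open within the stated total.** Suppose Levels 1 and -1 each fail with 6 subjects and Level -2 is the MTD. Then 4 + 12 + 6 + 12 = 34, the stated maximum, with 18 subjects treated at the MTD.
- **That the total could reach 4 + 36 + 18 = 58.** This repeats the plan's double count. With the counting rule the maximum is 52.

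Two further replies are fair. The extreme is remote: under the rates and readings above, establishing Level -5 with exactly 36 run-in subjects has probability of at most 0.35%. Reading B's threshold of 2 of 3 is also not written in the plan, which is why reading A is shown beside it.

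It could also be said that the Expansion is described as an additional cohort, so that 18 new subjects are meant and 28-34 is right for a run-in of 6-12. On that reading the crediting sentence that follows would have no effect. The two statements still need to be reconciled.

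None of this rescues the stated total. An expected range of 6-12 gives an expected total of 22-28 under the plan's own counting rule.

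**Conclusion.** The point holds as a mismatch in the stated size. The total of 28-34 counts six subjects twice. The plan's rules give 22-28 for a run-in of 6-12, and 37-52 if Level -5 is the MTD, before replacements. A run-in of 12 can establish an MTD at no more than three of the six levels, or two if each rejected level uses 6.

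The sizes assume that each rejected level uses 3 to 6 subjects, six are treated at the MTD, and the Expansion fills its 18. If a level closed after only two subjects, Level -3 would also fit within 12 (3 × 2 + 6 = 12).

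The probabilities rest wholly on assumed DLT rates. The chance of no MTD within 12 is about 1-3% at a flat 10%, 11-18% at a flat 20%, and 48-54% in the least favourable pattern shown. The chance of exceeding 34 or finding no MTD is smaller, from about 0-0.4% to 23-24%.

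This should be corrected, but it does not undermine the design. The documents do not support saying that levels are unreachable or that the Expansion cannot open.

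**What to change.** In the Synopsis (Methodology; Number of Subjects and Centers) and in Sections 5.1 and 5.2:

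1. Say that 6-12 is the expected size of the Combination Run-in, and give the range that the table implies, 6 to 36.
2. Restate the study total with the counting rule: 22-28 expected, up to 52, plus replacements under Section 6.3.2.
3. Show the sum once, as 4 + run-in + 12, so that a reader can see that the MTD subjects are counted once.

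If the sponsor instead intends 12 as a limit, the dose table, the run-in size and the Expansion text in the Synopsis and Section 5.1 must be reconciled with it, and the plan must say what follows if the limit is reached without an MTD. The footnote's 1-of-3 trigger and the MTD definition of at most 1 of 6 also treat a single early DLT differently and should be reconciled, because the choice changes the run-in size. No dose level or stopping rule is proposed here.

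The cost is protocol wording and a different stated enrolment range. The first option leaves the dose levels and the primary test unchanged.

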## **Protocol Number: STX-101-02**

Safety Endpoints and Analyses: Safety endpoints for AEs include the following: incidences of all treatment-emergent adverse events (TEAEs) and all serious adverse events (SAEs); incidences of TEAEs and SAEs by severity; incidences of TEAEs and SAEs by relationship to study medications; incidences of all Grade 3 and 4 TEAEs and by severity and relationship to study medications; and discontinuation of subjects from the study due to AEs or death. Safety endpoints for AEs, clinical laboratory tests, vital signs, ECGs and physical examinations will be specified in the statistical analysis plan. All safety endpoints will be summarized separately for monotherapy and combination therapy phases of the study using descriptive statistics.

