#### 10.3.1.8. 7.1.8. Ongoing Safety Evaluation

A study safety evaluation will be conducted on a regular (monthly) basis by teleconference. Dose exposure, dose-limiting toxicity, AE/SAE profiles and clinical laboratory abnormalities, and other safety measures will be reviewed during each convened meeting. Subject accrual will not be interrupted during the regular scheduled safety evaluations. These discussions will be led by the Spirita Oncology Medical Monitor and Principal Investigator.

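### The DLT count rules cover only the Combination Run-in: no DLT rate over all subjects treated at the MTD is planned, pooling with the selected run-in six biases toxicity low, and the text does not say whether Expansion DLTs can change the MTD

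*Combined protocol and SAP*

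**What the plan says.** The enrolment limit appears in the Synopsis (Methodology), Section 5.1 and Section 5.5.1.2. It applies when a DLT occurs in two or more "of 6 subjects in the Combination Safety Run-in Phase during Cycle 1, no further subjects will be enrolled at that dose level". The sentence names both the phase and the cycle.

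The MTD definition follows: "The maximum tolerated dose (MTD) is defined as the doses of E6201 plus dabrafenib at which" no more than 1 of 6 subjects has a DLT. That sentence names no phase, but two others tie it to the run-in. One reads "A total of 6 subjects will be treated at the combined MTD doses for both drugs in the Combination Safety Run-in Phase" before Expansion begins. The other has Expansion dosed at the MTD determined in the run-in: "an additional cohort of up to N=18 subjects will be treated at the E6201 plus dabrafenib combined MTD". Run-in subjects treated at the MTD count towards Expansion accrual.

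The footnote to the dose-level table states a second count rule for moving to a lower level: 1 or more of 3, or 2 or more "of 6 subjects experience DLT at the previous dose level". It too concerns the choice of run-in level.

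For Expansion, the Safety Review Committee (SRC) "will review data from the Expansion Phase on an ongoing basis". Section 10.3.1.8 has a monthly teleconference that reviews DLTs among other measures and adds: "Subject accrual will not be interrupted during the regular scheduled safety evaluations". Section 5.6 allows the study to be halted for unacceptable risk, and individual dose reductions apply.

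On analysis, the Synopsis says: "All safety endpoints will be summarized separately for monotherapy and combination therapy phases of the study using descriptive statistics". Section 11.3.1.1 adds adverse event summaries by dose cohort and overall. Neither place lists DLT incidence.

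**The concern.** Six subjects say little about a DLT rate. Up to 12 more subjects at the same dose (up to 18 on another reading of the sample size) are the best information the trial will have on whether the run-in choice was sound. The supplied text gives their DLTs no stated role in judging the MTD and plans no DLT rate that includes them.

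There is also a reporting bias. The six run-in subjects at the MTD are not a random sample of toxicity at that dose: had two of them had DLTs, the dose would not be the MTD. A combination or dose-cohort table that merges them with the Expansion subjects therefore understates toxicity on average. The Expansion subjects are the unselected group, and no table is planned that shows them alone.

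At stake is how far the reported tolerability of the combination, a secondary objective, can be trusted when the dose is carried forward.

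**Working it through.** The plan gives no operating characteristics for its DLT rule, so there is no stated figure to reproduce.

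**Inputs.** Run-in n = 6; pass if 0 or 1 DLT (Synopsis; Sections 5.1 and 5.5.1.2). Main case: 12 further subjects, because run-in subjects at the MTD count towards the 18. The total N = 28 - 34 (4 + 6 + 18 to 4 + 12 + 18) instead adds all 18 on top, so 18 further subjects is the alternative. The text says up to 18, so neither number is a minimum. The true DLT rate p is not in the documents; 20%, one third and 40% are assumed.

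**Step 1, chance that a dose passes the run-in.** P(pass) = (1-p)^6 + 6p(1-p)^5.
- p = 0.20: 0.2621 + 0.3932 = 0.655
- p = 1/3: 0.0878 + 0.2634 = 0.351
- p = 0.40: 0.0467 + 0.1866 = 0.233

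If the footnote's 3-subject step is applied strictly (0 of 3, then at most 1 in the next 3), P(pass) = (1-p)^3 × [(1-p)^3 + 3p(1-p)^2]. At 0.40 this is 0.216 × 0.648 = 0.140.

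**Step 2, what a pass shows.** The exact one-sided 95% upper limit for the DLT rate is 39% after 0 of 6 and 58% after 1 of 6.

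**Step 3, selection bias after a pass.** Given at most 1 DLT in 6, the expected run-in count is 6p(1-p)^5 / [(1-p)^6 + 6p(1-p)^5] = 6p/(1+5p). The 12 further subjects contribute 12p. Pooled mean rate = [6p/(1+5p) + 12p]/18.

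| True rate | Mean DLTs in run-in six | Mean rate in the six | Expected DLTs in 12 | Pooled mean, 18 | Pooled mean, 24 (18 further) |
|---|---|---|---|---|---|
| 20% | 0.60 | 10.0% | 2.4 | 3.00/18 = 16.7% | 4.20/24 = 17.5% |
| 33% | 0.75 | 12.5% | 4.0 | 4.75/18 = 26.4% | 6.75/24 = 28.1% |
| 40% | 0.80 | 13.3% | 4.8 | 5.60/18 = 31.1% | 8.00/24 = 33.3% |

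The Expansion-only rate averages the true rate in each row.

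**Step 4, how often the full count would contradict the run-in.** The run-in limit of 2 in 6 is one third, which is 6 in 18. P(pass and at least 6 of 18) = P(0 of 6) × P(at least 6 of 12) + P(1 of 6) × P(at least 5 of 12).
- p = 0.40: 0.0467 × 0.3348 + 0.1866 × 0.5618 = 0.120
- p = 1/3: 0.0878 × 0.1777 + 0.2634 × 0.3685 = 0.113
- p = 0.20: 0.2621 × 0.0194 + 0.3932 × 0.0726 = 0.034

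Given a pass, the chance at 40% is 0.120/0.233 = 52%. With the strict 3-subject step the unconditional figures fall to 6.8% at 40% and 1.9% at 20%.

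**The case against.** The strongest reply is that Expansion is controlled. The SRC reviews its data continuously, DLTs are on the monthly agenda, Section 5.6 permits termination, and subjects have individual dose reductions. The sentence on accrual says only that it is not held routinely for a scheduled meeting; it does not forbid a pause because of what the meeting finds. All of this stands. A reader might infer that Expansion is unmonitored, or that a dose well above the limit would inevitably be enrolled in full and reported as the MTD. The documents do not support that, since it requires the SRC, the Medical Monitor and the sponsor all to take no action.

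Nor are the Expansion subjects discarded. They are in the full analysis set (Section 11.2), and their adverse events are summarised by dose cohort, severity and relationship, with listings and narratives. What is missing is a DLT rate and a display separate from the selected six.

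The Synopsis also defers details of the safety endpoints to a statistical analysis plan. The supplied text contains only protocol Section 11, so a DLT table may exist elsewhere. The finding is limited to what was supplied.

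Finally, the larger percentages are conditional on an assumed high rate and on a pass. That is fair, and the unconditional figures are given for that reason. The selection bias is modest at a true 20% (16.7% against 20%).

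**Conclusion.** The point holds as a gap in analysis and wording. Both count rules are confined to the run-in and do not match: 1 DLT in the first 3 subjects moves the dose down under the footnote, while 1 in 6 is compatible with the MTD in the text. Expansion DLTs have no planned rate, and the text does not say whether they can change the declared MTD.

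The bias from pooling is certain in direction. Its size is about 3 percentage points at a true 20%, 7 at 33% and 9 at 40%, assuming 6 + 12 subjects, independent outcomes and the same true rate in both phases. It is somewhat smaller with 18 further subjects. The chance that a dose passes and the full count then reaches the run-in's own proportion is 12% at a true 40% and 3.4% at 20%.

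A reader might go further and infer that the plan needs a numerical enrolment limit in Expansion. The documents contain no such limit and no figure from which to derive one. Whether to set one is a clinical decision for the sponsor and the SRC, and none is proposed here. This is a cheap improvement, not a fatal flaw.

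**What to change.** 1. In Section 11.3.1, count Cycle 1 DLTs in every subject started at the MTD level, run-in and Expansion together, and report the rate with an exact 95% CI beside the run-in MTD declaration. State the denominator, because Section 6.3.2 replaces some subjects who do not complete Cycle 1.
2. Show Expansion-only DLT and Grade 3 or higher TEAE rates beside the pooled rates, with a note that the run-in six at the MTD are selected for having at most 1 DLT.
3. Reconcile the DLT and MTD passages (Synopsis Methodology, the dose-table footnote, Sections 5.1 and 5.5.1.2) with each other and with the ongoing Expansion review (Synopsis, Sections 5.1 and 10.3.1.8). It should be clear whether the SRC judges the MTD on the cumulative DLT count. Any threshold, and any action, stays with the sponsor and the SRC.

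The cost is one extra table and a wording change; DLTs are already reviewed monthly. The downside for the sponsor is a reported DLT rate that may look less favourable than the pooled one.
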